### **2.3 PHARMACOKINETIC OBJECTIVE**

The PK objective for this study is to characterize the PK profiles of obinutuzumab, *rituximab*, polatuzumab vedotin, and lenalidomide when given in combination on the basis of the following endpoints:

- Observed serum obinutuzumab concentration at specified timepoints
- *Observed serum rituximab concentration at specified timepoints*
- Observed serum and plasma concentrations of polatuzumab vedotin and relevant analytes (TAb, acMMAE, and unconjugated MMAE) at specified timepoints
- Observed plasma lenalidomide concentration at specified timepoints

### **2.4 IMMUNOGENICITY OBJECTIVES**

The immunogenicity objective for this study is to evaluate the immune response to obinutuzumab, *rituximab*, and to polatuzumab vedotin on the basis of the following endpoints:

- Incidence of human anti-human antibodies (HAHAs) to obinutuzumab during the study relative to the prevalence of HAHAs at baseline
- *Incidence of human anti-chimeric antibodies (HACAs) to rituximab during the study relative to the prevalence of HACAs at baseline*
- Incidence of ATAs to polatuzumab vedotin during the study relative to the prevalence of ATAs at baseline

The exploratory immunogenicity objective for this study is to evaluate potential relationships between HAHAs *or HACAs*, and ATAs on the basis of the following endpoint:

- Correlation between HAHA *or HACA*, and ATA status and *respective* efficacy, safety, or PK endpoints

## 2.5 BIOMARKER OBJECTIVE

The exploratory biomarker objective for this study is to identify non-inherited biomarkers that are predictive of response to study treatment (i.e., predictive biomarkers), are associated with progression to a more severe disease state (i.e., prognostic biomarkers), are associated with acquired resistance to study treatment, are associated with susceptibility to developing adverse events, can provide evidence of study treatment activity, can increase the knowledge and understanding of lymphoma biology or study treatment mechanism of action, or can contribute to improvement of diagnostic assays on the basis of the following endpoint:

- Association between non-inherited biomarkers (listed in Section 4.5.6) and efficacy, safety, pharmacokinetics, or immunogenicity endpoints

## 3. STUDY DESIGN

### 3.1 DESCRIPTION OF STUDY

#### 3.1.1 Overview of Study

This Phase Ib/II, open-label, multicenter, non-randomized, dose-escalation study will evaluate the safety, efficacy, and pharmacokinetics of G+Pola+Len in patients with R/R FL and *R +Pola +Len in patients with R/R DLBCL*.

The study will include an initial dose-escalation phase followed by an expansion phase, during which polatuzumab vedotin and lenalidomide will be given at their RP2Ds (see Sections 3.1.2 and 3.1.2.2).

Approximately 110–128 patients are expected to be enrolled in this study, at approximately 20–25 investigative sites worldwide.

[figure not shown]
All patients will be closely monitored for adverse events throughout the study and for at least 90 days after the last dose of study treatment (see Section 5.3.1). Adverse events will be graded according to the National Cancer Institute Common Terminology Criteria for Adverse Events (NCI CTCAE), Version 4.0. An Internal Monitoring Committee (IMC) will be established to monitor patient safety throughout the study (see Section 3.1.4).

To characterize the PK properties of obinutuzumab, *rituximab*, polatuzumab vedotin, and lenalidomide, blood samples will be obtained at various timepoints before and during study treatment administration.

Response will be determined by the IRC (see Section 3.1.5) and the investigator using the Lugano 2014 criteria. The primary efficacy endpoint will be based on IRC assessment of response. Refer to Section 4.5.5 for details on tumor assessments.

Schedules of assessments are provided in Appendix 1, Appendix 2, and Appendix 3. The Lugano Response Criteria are provided in Appendix 5.

**Figure 1 Study Schema**

C=cycle; CR=complete response; D=day; DLBCL=diffuse large B-cell lymphoma; EOI=end of induction; FL=follicular lymphoma; G=obinutuzumab; Len=lenalidomide; PO=by mouth; Pola=polatuzumab vedotin; PR=partial response; QD=every day; Q2M=every 2 months; R=rituximab; RP2D=recommended Phase II dose; SD=stable disease.

Notes: Each cycle is 28 days. A month is defined as 28 days.

a FL patients enrolled in the dose-escalation phase who achieve a CR, PR, or SD at EOI may receive maintenance treatment with G + Len following the maintenance schedule outlined for patients with FL during the expansion phase.

b Maintenance and consolidation treatment should start 8 weeks ( $\pm 1$  week) after Day 1 of Cycle 6.

c DLBCL patients enrolled in the dose-escalation phase who achieve a CR or PR at EOI may receive consolidation treatment with R + Len following the maintenance schedule outlined for patients with DLBCL during the expansion phase.

### **3.1.2**            *Obinutuzumab plus Polatuzumab Vedotin plus Lenalidomide Treatment Group (Patients with Follicular Lymphoma)*

#### **3.1.2.1**        **Dose-Escalation Phase**

The purpose of the *FL* dose-escalation phase is to identify the RP2D for polatuzumab vedotin and the RP2D for lenalidomide when combined with a fixed dose of obinutuzumab as induction treatment. *This* dose-escalation phase will include *FL* patients only; these patients may receive post-induction treatment if eligible (see Section 3.3.1).

Approximately 18–30 patients will be enrolled in the *FL* dose-escalation phase. Cohorts of 3–6 patients each will be treated in accordance with the treatment regimens and dose-escalation rules described in Section 3.1.2.1.3.

Patients will be closely monitored for adverse events during the DLT assessment window, defined as the first treatment cycle (from Day 1 of Cycle 1 to Day 1 of Cycle 2). Adverse events meeting the criteria for DLT, as defined below (see Section 3.1.2.1.1), will be reported to the Sponsor within 24 hours (see Section 5.4.2).

Patients experiencing a DLT during the DLT assessment period *may continue receiving study treatment once the event has resolved, if determined by investigator in consultation with Sponsor that it is safe to continue treatment and there is potential for clinical benefit in their judgment.*

Patients who discontinue from the study prior to completing the DLT assessment window for reasons other than a DLT will be considered non-evaluable for dose-escalation decisions and RP2D assessments and will be replaced by an additional patient at that same dose level. Patients who miss 1 or more doses of polatuzumab vedotin *or obinutuzumab* or 5 consecutive daily doses of lenalidomide during the DLT assessment window for reasons other than a DLT will also be replaced *and considered non-evaluable for dose-escalation decisions.* Patients who receive supportive care during the DLT assessment window that may confound the evaluation of DLTs may be replaced at the discretion of the Medical Monitor.

##### **3.1.2.1.1**      **Definition of Dose-Limiting Toxicity**

In this study, a DLT is defined as any one of the following events occurring during the first cycle of treatment and assessed by the investigator as related to study treatment *that is not attributed to disease progression or another clearly identified cause:*

- *Any adverse* event of any grade that leads to a delay of > 14 days in the start of the next treatment cycle
- *Any* Grade 3 or 4 non-hematologic adverse event, with the following exceptions:
  - Grade 3 or 4 IRRs

Note that IRRs may occur even after a small amount of drug has been administered (i.e., IRRs are not dose dependent).

- Grade 3 diarrhea that responds to therapy within 72 hours
- Grade 3 nausea or vomiting that occurs in the absence of premedication and responds to adequate therapy within 72 hours
- *Grade 3 laboratory TLS without manifestations of clinical TLS (i.e., creatinine  $\geq 1.5 \times$  upper limit of normal (ULN) and/or renal dysfunction, cardiac arrhythmias, seizures, or sudden death) that resolves within 7 days (see [Appendix 12](#))*
- *Grade 3 fatigue that resolves to Grade  $\leq 2$  within 7 days*
- *Grade 3 laboratory abnormality that is asymptomatic and deemed by the investigator not to be clinically significant*
- *Grade 3 elevation in ALT or AST, provided the following criteria are met:*
  - ALT or AST level is no greater than  $8 \times$  ULN*
  - ALT or AST elevation resolves to Grade  $< 2$  ( $< 5$  ULN) within 7 days*
  - Total and direct bilirubin and other laboratory parameters of liver synthetic function (e.g., prothrombin time) are normal*
  - No clinical signs or symptoms of hepatic injury*
- *Any increase in hepatic transaminase  $> 3 \times$  baseline AND an increase in direct bilirubin  $> 2 \times$  ULN, WITHOUT any findings of cholestasis or jaundice or signs of hepatic dysfunction AND in the absence of other contributory factors (e.g., worsening of metastatic disease or concomitant exposure to known hepatotoxic agent or of a documented infectious etiology) is suggestive of potential drug-induced liver injury (according to Hy's Law) and will be considered a DLT.*
- *In patients with Grade 1 ALT or AST elevation at baseline as a result of liver metastases, only a Grade  $\geq 3$  elevation that is also  $\geq 3 \times$  baseline lasting  $> 7$  days will be considered a DLT.*
- Hematologic adverse event that meets any of the following criteria:
  - Grade 3 or 4 neutropenia in the presence of sustained fever of  $> 38^\circ\text{C}$  (lasting  $> 5$  days) or a documented infection
  - Grade 4 neutropenia lasting  $> 7$  days
  - Grade 3 or 4 thrombocytopenia that results in significant bleeding per investigator judgment
  - Grade 4 thrombocytopenia lasting  $> 7$  days

Other toxicities occurring during the first cycle that are considered to be clinically relevant and related to study treatment, as determined by the investigator and the Medical Monitor may also be considered DLTs.

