### **5.2.3 Adverse Events of Special Interest (Immediately Reportable to the Sponsor)**

Adverse events of special interest are required to be reported by the investigator to the Sponsor immediately (i.e., no more than 24 hours after learning of the event; see Section 5.4.2 for reporting instructions). Adverse events of special interest for this study include the following:

- Cases of potential drug-induced liver injury that include an elevated ALT or AST in combination with either an elevated bilirubin or clinical jaundice, as defined by Hy's law (see Section 5.3.5.7)
- Suspected transmission of an infectious agent by the study treatment, as defined below:

Any organism, virus, or infectious particle (e.g., prion protein transmitting transmissible spongiform encephalopathy), pathogenic or non-pathogenic, is considered an infectious agent. A transmission of an infectious agent may be suspected from clinical symptoms or laboratory findings that indicate an infection in a patient exposed to a medicinal product. This term applies only when a contamination of any of the study treatment components is suspected.
- TLS of any grade, irrespective of causality
- *Second malignancies*

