#### **5.3.5.7 Abnormal Liver Function Tests**

The finding of an elevated ALT or AST ( $>3 \times$  baseline value) in combination with either an elevated total bilirubin ( $>2 \times$  ULN) or clinical jaundice in the absence of cholestasis or other causes of hyperbilirubinemia is considered to be an indicator of severe liver injury (as defined by Hy's law). Therefore, investigators must report as an adverse event the occurrence of either of the following:

- Treatment-emergent ALT or AST  $>3 \times$  baseline value in combination with total bilirubin  $>2 \times$  ULN (of which  $\geq 35\%$  is direct bilirubin)
- Treatment-emergent ALT or AST  $>3 \times$  baseline value in combination with clinical jaundice

The most appropriate diagnosis or (if a diagnosis cannot be established) the abnormal laboratory values should be recorded on the Adverse Event eCRF (see Section 5.3.5.2) and reported to the Sponsor immediately (i.e., no more than 24 hours after learning of the event), either as a serious adverse event or a non-serious adverse event of special interest (see Section 5.4.2).

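### The Hy's-law DLT criterion in Section 3.1.2.1.1 excludes patients with jaundice, whom Sections 5.3.5.7 and 5.2.3 count as Hy's-law cases, so a narrow class of liver events is a DLT only by discretion

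*Combined protocol and SAP*

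**What the plan says.** Section 3.1.2.1.1 defines a DLT for FL, and Section 3.1.3.1 refers to it for DLBCL. An event must fall in Cycle 1, be judged related by the investigator, and not be put down to progression or another identified cause.

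The liver-injury bullet takes a transaminase above 3 times baseline with direct bilirubin above 2 times ULN, "WITHOUT any findings of cholestasis or jaundice or signs of hepatic dysfunction AND in the absence of other contributory factors". It invokes Hy's law and makes a qualifying case a DLT by rule.

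Section 5.3.5.7 gives the protocol's working definition under the same name: ALT or AST above 3 times baseline with either total bilirubin above 2 times ULN "or clinical jaundice in the absence of cholestasis or other causes of hyperbilirubinemia is considered to be an indicator of severe liver injury". Its reporting instruction adds that at least 35% of the bilirubin should be direct on the laboratory limb. Section 5.2.3 repeats the structure for events of special interest: "elevated ALT or AST in combination with either an elevated bilirubin or clinical jaundice, as defined by Hy's law".

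The other rule-based routes open to a liver event are the general criterion, "Grade 3 or 4 non-hematologic adverse event, with the following exceptions", and any "event of any grade that leads to a delay of > 14 days in the start of the next treatment cycle". The exception for Grade 3 ALT/AST elevation applies only if, among other conditions, "Total and direct bilirubin and other laboratory parameters of liver synthetic function (e.g., prothrombin time) are normal" and there is no clinical evidence of hepatic injury. Remaining clinically relevant related toxicities, "as determined by the investigator and the Medical Monitor may also be considered DLTs".

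**The concern.** The two definitions carry one label and treat jaundice in opposite ways. In Sections 5.3.5.7 and 5.2.3 it helps to establish the case; in the DLT bullet it removes the case. Read literally, a patient whose laboratory values make a mandatory DLT loses that status on becoming jaundiced, so the clinically worse presentation has the weaker claim to be counted.

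DLT incidence in Cycle 1 is the stated endpoint for choosing the RP2D in both histologies (Section 2.1), and the 3+3 rules act on single events. Lenalidomide, the drug escalated in both histologies, carries a hepatotoxicity warning in Section 5.1.4.7, and Section 5.1.3.2 reports hepatotoxicity with polatuzumab vedotin. Whether a jaundiced Hy's-law case counts should not vary from cohort to cohort.

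**Working it through.** There is no planned figure to reproduce, because this is a question of definitions. The check puts a case through each rule-based criterion and then follows the count through the 3+3 rules.

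**1. A worked case.** Take a related event in Cycle 1: ALT 4 x ULN from a baseline of 0.8 x ULN (4 / 0.8 = 5 times baseline), total bilirubin 2.8 x ULN, direct bilirubin 2.2 x ULN, no cholestasis or other cause, Cycle 2 delayed by 14 days or less. The protocol does not print the CTCAE cut-offs, so assume that Grade 3 starts above 5 x ULN for ALT/AST (suggested by a parenthesis in the ALT/AST exception) and above 3 x ULN for bilirubin.

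| Criterion | Without jaundice | With jaundice |
|---|---|---|
| Section 3.1.2.1.1 liver bullet | met, DLT by rule | not met |
| Grade 3-4 non-hematologic | not met on laboratory grades | not met on laboratory grades |
| Delay of more than 14 days | not met | not met |
| Section 5.3.5.7 jaundice limb | not applicable | met, whatever the direct fraction |
| Result | mandatory DLT | discretionary only |

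**2. Sensitivity to the cut-offs.** The gap persisted with the bilirubin Grade 3 cut-off set at 2.5, 3 or 5 x ULN; at 2.5, lower total bilirubin in the example to 2.2 x ULN. For ALT/AST, with the lower edge of Grade 3 at E x ULN, a value can exceed 3 times baseline and stay below Grade 3 only if 3 x baseline < E x ULN, that is baseline < E/3. At E = 5 this is 5/3 = 1.67 x ULN; at a lower assumed edge of E = 3 it is 1.0 x ULN. Section 4.1.2 admits baselines up to 2.5 x ULN, so some patients lie inside the window and some outside.

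**3. What the other routes already catch.** A jaundiced case with Grade 3-4 ALT, AST or bilirubin is a DLT under the general criterion: raised bilirubin and clinical signs defeat the ALT/AST exception, and symptoms defeat the exception for asymptomatic laboratory findings. A case that delays Cycle 2 by more than 14 days counts at any grade. What is left is jaundice with no Grade 3-4 component and timely recovery.

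**4. The bilirubin triggers.** Write T and D for the laboratory's total and direct ULN. Total above 2T with at least 35% direct means direct above 0.35 x 2T = 0.70T. That is sure to exceed 2D only if D is at most 0.35T, which the protocol does not state. Conversely, direct can exceed 2D while total stays at or below 2T. Neither trigger contains the other, so there is also a smaller mismatch without jaundice.

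**5. Effect of one uncounted event (Sections 3.1.2.1.3 and 3.1.3.1).** If the patient stays evaluable, 1/3 becomes 0/3, or 2/6 becomes 1/6. Let p be an assumed DLT rate in further patients.

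- *Event in the first three, other two clean.* Counted: three more clean patients are needed, (1-p)^3. Uncounted and kept: the dose clears. Uncounted and replaced: (1-p) + p(1-p)^3.
- *Event in patients 4-6 of a cohort already at 1/3, other two of those clean.* Counted: 2/6, intolerable. Uncounted and kept: 1/6, clears. Uncounted and replaced: 1-p.

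| p | First three: counted / kept / replaced | Patients 4-6: counted / kept / replaced |
|---|---|---|
| 10% | 73% / 100% / 97% | 0% / 100% / 90% |
| 20% | 51% / 100% / 90% | 0% / 100% / 80% |
| 30% | 34% / 100% / 80% | 0% / 100% / 70% |

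Entries are the chance that the dose clears, given the event and given that the discretionary clause is not used. They say nothing about how often that happens.

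**The case against.** **Jaundice may be listed as a competing explanation.** The bullet goes on to exclude other contributory factors, with examples that are all alternative causes, so the earlier items might be meant the same way. This does not hold up. Signs of hepatic dysfunction are a consequence of liver injury and not a rival cause; the ALT/AST exception in the same section treats clinical signs as making an event more countable; and Section 5.3.5.7 excludes only cholestasis and other causes.

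**The event may be graded as a diagnosis.** Sections 5.3.5.2 and 5.3.5.7 ask for the diagnosis in preference to component findings, and Table 21 grades a severe or medically significant event not listed in CTCAE as Grade 3. A recorded liver-injury diagnosis could thus be a DLT under the general criterion. This stands, and it narrows the gap further.

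**Safeguards are strong.** The case is reportable within 24 hours as an event of special interest. The Medical Monitor, who shares the discretionary call, also makes the escalation decision after reviewing safety data; the Sponsor can halt escalation; and the IMC approves the RP2D. A missed case is unlikely. These steps remain judgements and do not make the event a DLT by rule.

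**Replacement is not clearly triggered.** A reader might infer that an uncounted patient would be declared non-evaluable for missing five consecutive lenalidomide doses, so that the event leaves the data altogether. The documents do not clearly require such a hold for a Grade 2 or lower liver event: Table 19 withholds for ALT, AST or bilirubin from Grade 3, its Grade 2 row covers toxicities not described elsewhere in the table, and Section 5.1.7.2 treats Grade 2 or lower as recovered. The replacement column is illustration only.

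**Conclusion.** The liver bullet is wrong as written, within a narrow scope. It gives the wrong classification for a related Hy's-law case with jaundice when nothing in it, including any recorded liver-injury diagnosis, reaches Grade 3-4 and Cycle 2 is not delayed by more than 14 days. Such a case is a DLT only by discretion. The documents give no rate; it should be rare, and unlikely to go unnoticed. The consequence, if one is not counted and the patient stays evaluable, is one fewer DLT in a cohort of three or six, which can be enough to clear a dose that would otherwise be expanded or stopped.

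This rests on a literal reading of the bullet and on assumed CTCAE cut-offs; the conclusion did not change over the bilirubin range tried, and the ALT/AST window stays open at both edges tried.

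Two stronger readings are not supported. One is that jaundiced drug-induced liver injury generally escapes the DLT count: cases with a Grade 3-4 component or a long delay are caught. The other is that treatment-related deaths go uncounted because the general criterion stops at Grade 4. Most fatal events pass through a countable Grade 3-4 phase, and the IMC monitors deaths. The main remainder is a fatal infusion reaction, whose Grade 3-4 phase is excepted on the stated ground, "i.e., IRRs are not dose dependent". Section 5.1.2.1 puts fatal rituximab reactions between 1 in 10,000 and 1 in 1,000. By 1-(1-r)^n, that is a 0.12% to 1.2% chance of any among 12 DLBCL escalation patients, and 0.18% to 1.8% among 18. With P(p) = (1-p)^3 + 3p(1-p)^5 as the chance that a dose clears, P(p-r) - P(p) at an assumed p of 20-33% is about 0.02 to 0.2 percentage points. The documents give no corresponding rate for obinutuzumab. This is a wording matter only.

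**What to change.** In Section 3.1.2.1.1:

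- Keep the existing trigger on direct bilirubin above 2 times ULN.
- Delete jaundice and signs of hepatic dysfunction from the exclusion, leaving cholestasis and other contributory factors.
- Add the two Section 5.3.5.7 limbs: ALT or AST above 3 times baseline with total bilirubin above 2 times ULN, at least 35% of it direct; or with clinical jaundice; each in the absence of cholestasis or another cause of hyperbilirubinemia. Adding these to the direct-bilirubin trigger, without replacing it, ensures that no current DLT is lost.
- As a minor clean-up, word the general non-hematologic criterion as Grade 3 or higher. Whether a fatal infusion reaction should count against the escalated dose is for the sponsor to decide, since in DLBCL only lenalidomide is escalated.

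The change is confined to one section and reaches DLBCL through the existing cross-reference. Total and direct bilirubin, ALT and AST are already in the Section 4.5.6 chemistry panel. The downside is an occasional expansion of a cohort by three patients.

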### **3.1.2.1.2 Treatment Regimens for the Follicular Lymphoma Dose-Escalation Phase**

All patients enrolled in the dose-escalation phase will receive induction treatment, administered in 28-day cycles as shown in [Table 1](#). When study treatments are given on

the same day, they will be administered sequentially in the following order: lenalidomide, obinutuzumab, and polatuzumab vedotin.

**Table 1 Induction Treatment for the *Follicular Lymphoma* Dose-Escalation Phase**

Cycle	G+Pola+Len (28-Day Cycles)
Cycle 1	
 
• Lenalidomide 10 mg, 15 mg, or 20 mg PO once daily on Days 1–21
 
• Obinutuzumab 1000 mg IV on Days 1, 8, and 15
 
• Polatuzumab vedotin 1.4 mg/kg or 1.8 mg/kg IV on Day 1
 

Cycles 2–6	
 
• Lenalidomide 10 mg, 15 mg, or 20 mg PO once daily on Days 1–21
 
• Obinutuzumab 1000 mg IV on Day 1
 
• Polatuzumab vedotin 1.4 mg/kg or 1.8 mg/kg IV on Day 1
 

*G + Pola + Len* = obinutuzumab in combination with polatuzumab vedotin and lenalidomide; IV=intravenous; PO=by mouth.

Note: Treatments will be administered sequentially in the following order: lenalidomide, obinutuzumab, and polatuzumab vedotin.

Patients who achieve a CR, a PR, or stable disease at EOI will receive maintenance treatment with G+Len, as outlined in [Table 2](#). Polatuzumab vedotin will not be given as maintenance treatment. Maintenance treatment should start 8 weeks ( $\pm 1$  week) after Day 1 of Cycle 6 and will continue until disease progression or unacceptable toxicity for up to 24 months.

